### **G. Statistical Power Justification**

**Primary endpoint.** The primary endpoint of this study is the 1-year overall survival (OS) which will be compared to historical data (1-year OS=25%). Assuming survival times following an exponential distribution and an additional 1-year follow-up period after the accrual period, a total of 60 patients will be enrolled and this allows us 85% power at 1-sided  $\alpha=0.05$  to detect 15% difference (40% vs. 25%) in 1-year OS.

**Secondary endpoints.** A power analysis was performed using two-sample t-test for between-group difference and paired t-test for the change over time. For tumor clearance, this will provide > 99% power to detect a 10% difference in the means at two separate time points for clones with 6 or more variants, and > 98% power to detect a 15% difference if there are 3 or more variants per clone with  $\alpha = 0.05$  (power will decrease to 91% and 82%, respectively, in cases where the standard deviation is 4.7%, the maximum we have observed thus far). For pharmacologic correlations, we anticipate 85% power to determine a 25 ng/ml difference between the average Cmax of 45 evaluable responders and 55 evaluable non-responders with an anticipated average Cmax of 70 ng/ml and a standard deviation of 40 ng/ml within the entire cohort, and with  $\alpha = 0.05$ . We believe a less significant difference would not be sufficient to warrant application in clinical decision making (i.e. whether to continue therapy for more than 1 cycle). We anticipate 99% power to determine a difference of 20% in the reduction of bone marrow methylcytosine between 45 evaluable responders and 55 evaluable non-responders with an expected standard deviation of 15% and  $\alpha = 0.05$ . The difference in methylcytosine reduction previously observed was 30% between patients achieving CR/PR and those with only hematologic improvement.

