## **15.0 STATISTICAL CONSIDERATIONS**

### **15.1 Study design and Sample size**

This will be an open-label single-arm phase II trial. The primary endpoint of this study is the 1-year overall survival (OS) which will be compared to historical data. *TP53* mutations occur in 10-15% of patients with AML, and tend to occur in older adults. Our power analysis suggests that we need at least 60 total patients enrolled. We anticipate that 500-700 total AML patients will need to be available at enrolling institutions in order to reach the patient goal of 60. Time to complete accrual will be 24 months.

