#### **F. Secondary *Molecular Endpoints Analyses***

**Rate of patient specific mutation clearance** after 28, and 56 days of therapy will be determined using an Illumina based platform. We will compare the rate of mutation clearance between the patients who achieve a CR/CRi after 4 cycles and those who do not. We anticipate that we will identify between 6 and 25 exonic SNVs per case (the range obtained with >200 AML samples sequenced to date with whole genome or exome sequencing), and that the expected 95% confidence interval of the mean variant allele frequency will be  $\pm 2.56\%$  and  $\pm 1.25\%$ , respectively, if we assume an anticipated standard deviation of 3.2% within the same clone. The change of tumor burden over time and its association with clinical response will be assessed using 2-way ANOVA for repeated measurement data, followed by the ad-hoc multiple comparisons for between-group differences (e.g., responders vs. non-responders) at given time points as well as the between-time differences within each group. The resultant critical P values will also be corrected using permutation analysis for multiple testing.

The percent decrease in bone marrow methylcytosine will be calculated on day  $10 \pm 1$ . We will compare this reduction with previously published data and between the patients who achieve CR/CRi and those who do not. The correlation of peak plasma levels of decitabine with response will be assessed using 2-sample t-test or Mann-Whitney non-parametric rank-sum test as appropriate. The change of total bone marrow DNA methylcytosine from baseline and its association with both steady-state plasma drug levels and response will be assessed using 2-way ANOVA for repeated measurement data, followed by the ad-hoc multiple comparisons for between-group differences (e.g., responders vs. non-responders) and between-time

differences. Similar analyses will be performed for the correlation of expression profiles and SNP analysis with pharmacokinetic data.

The proportion of patients who achieve mutation clearance to <0.1%, after 3 cycles of decitabine, will be calculated and its 2-sided 90% confidence interval (CI) will also be provided. Using a sensitive sequencing technology such as Haloplex, the sensitivity of PB or BM for detecting residual mutation burden, as well as the *TP53* clonal burden reduction after consolidation with stem cell transplantation will be summarized using contingency tables.

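### The Cmax and methylcytosine power statements use 100 evaluable patients in a 60-patient trial; the stated 85% Cmax power is unattainable, and no listed sample supplies plasma drug levels

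*Combined protocol and SAP*

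**What the plan says.** On sample size, the primary-endpoint paragraph of Section 15.4.G says that "a total of 60 patients will be enrolled". Section 15.1 estimates how many AML patients must be available at the sites "in order to reach the patient goal of 60".

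On correlative power, the next paragraph of 15.4.G names the two-sample t-test for between-group differences and makes two statements at alpha 0.05:

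- **Cmax:** 85% power for a 25 ng/ml "difference between the average Cmax of 45 evaluable responders and 55 evaluable non-responders", with a standard deviation of 40 ng/ml in the whole cohort.
- **Methylcytosine:** 99% power for a "difference of 20% in the reduction of bone marrow methylcytosine between 45 evaluable responders and 55 evaluable non-responders", with a standard deviation of 15%.

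Neither statement gives the sidedness. The methylcytosine statement gives no time point.

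On analysis, Section 15.4.F plans three uses of plasma data:

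- "The correlation of peak plasma levels of decitabine with response will be assessed using 2-sample t-test" or a rank-sum test;
- for the change in marrow methylcytosine, "its association with both steady-state plasma drug levels and response will be assessed" by repeated-measures ANOVA;
- the "correlation of expression profiles and SNP analysis with pharmacokinetic data".

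The same section says "The percent decrease in bone marrow methylcytosine will be calculated on day" 10, and that the reduction will be compared between patients with and without CR/CRi.

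**The concern.** Two groups that total 100 cannot be formed from 60 patients, so both power statements describe comparisons that this trial cannot make. For Cmax the shortfall matters. A null result would be read against an 85% power that the design does not have, and 15.4.G itself defends the 25 ng/ml difference by its relevance to clinical decisions.

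The plasma analyses also appear to have no data behind them. If no plasma is drawn, the Cmax comparison cannot be made at any power. The documents do not show whether the plasma text or the sampling text is the one in error.

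**Working it through.** **Inputs, all from 15.4.G.** Total enrolment 60. Cmax: difference 25, SD 40. Methylcytosine: difference 20, SD 15. Alpha 0.05, two-sample t-test.

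**Formula.** Noncentrality δ = Δ / (σ√(1/n₁ + 1/n₂)), with n₁ + n₂ − 2 degrees of freedom. Power is the probability that a noncentral t with that δ falls beyond the critical value.

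**Step 1: group sizes.** 45 + 55 = 100, against 60 enrolled.

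**Step 2: reproduce the stated 85% for Cmax.** At 45/55, δ = 25 / (40√(1/45 + 1/55)) = 3.11 and the two-sided critical value is 1.984. Power is 86.8%. Allowing for the rank-sum test (sample size × 0.955) gives 85.3%. The stated figure therefore fits 100 patients and a two-sided test. One-sided, 45/55 would give 92.5%. With 40 read as the total SD, the two-sided figure would be 90.0%.

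**Step 3: Cmax with all 60 evaluable.** At 30/30, δ = 25 / (40√(2/30)) = 2.42 and the two-sided critical value is 2.002. Power is 66.3%, the maximum over all splits of 60.

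| Reading, 60 patients | Split | Power |
|---|---|---|
| Two-sided, SD within group | 30/30 | 66.3% |
| Two-sided, SD within group | 27/33 (the plan's 45:55 ratio) | 65.9% |
| Two-sided, SD within group | 20/40 (assumed) | 61.2% |
| Two-sided, SD within group | 15/45 (assumed) | 54.0% |
| Two-sided, SD 40 as total SD | 30/30 | 70.7% |
| One-sided, SD within group | 30/30 | 77.3% |
| One-sided, SD 40 as total SD | 30/30 | 80.9% |

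For the total-SD rows, the within-group variance is 40² − 0.25 × 25² = 1443.75, so the within-group SD is 38.0. The last row is the most favourable reading, and it also stays below 85%.

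**Step 4: what 85% would need.** The requirement is 94 patients (47/47) two-sided with SD within group, or 68 (34/34) on the most favourable reading. With 30/30 two-sided, 85% is reached only for a difference of about 31.5 ng/ml.

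**Step 5: methylcytosine.** At 45/55 the power exceeds 99.9%, so the stated 99% reads as a floor. At 27/33, δ = 20 / (15√(1/27 + 1/33)) = 5.14 and two-sided power is 99.9%. For near-equal groups, 99% needs 44 evaluable patients two-sided (22/22, 99.1%) or 37 one-sided (18/19, 99.0%). With all 60 evaluable, the smaller group must have at least 14 two-sided (14/46, 99.0%) or 12 one-sided (12/48, 99.3%).

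**Step 6: is there a source for plasma levels?**

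- Section 2 lists no pharmacokinetic objective.
- Section 9.2 lists marrow, peripheral blood, skin and buccal samples. Peripheral blood is processed to frozen cells, and only the cellular part of the marrow is kept.
- The visit procedures in 5.1, the calendar in Section 10 and the forms in Section 11 contain no plasma sample, no draw timed to the infusion and no pharmacokinetic form.
- Section 1.3.A gives plasma half-lives of about 7 minutes and 35 minutes for the two phases. A peak level therefore needs a timed draw, and the listed blood samples cannot be assumed to serve.

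**The case against.** **Section 15.1 speaks of a minimum of 60, so 100 might be possible.** This does not stand. 15.4.G gives 60 as the total, 15.1 calls 60 the goal, and nothing plans for more.

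**Sidedness and the meaning of SD 40 are open.** This stands as an ambiguity but does not rescue the figure. Granting both points in the sponsor's favour, with an equal split, gives 80.9%.

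**The plasma text may be right and the sampling text incomplete.** This stands. A reader might infer that the pharmacokinetic wording is left over and should simply go, but the documents do not settle which side is wrong.

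**The methylcytosine power survives.** This largely stands. A reader might infer from the impossible group sizes that the 99% is lost; near-equal splits of 60 keep it.

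**Day 10 marrow need not limit the methylcytosine number.** This stands in part. Sections 5.1.E and 9.2 restrict day 10 marrow to Washington University patients, and 15.4.F ties the responder comparison to the day 10 reduction. Day 10 is therefore the natural reading of the power sentence. But that sentence names no day, and 15.4.F also has a change-from-baseline analysis with no day given. Cycle 1 day 28 marrow carries no such site restriction. A reader should not conclude that the evaluable number is certainly below 60.

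**A much lower Cmax power could be argued from the 10%-15% historical response rate in Section 2.2.** The documents do not support using it as the expected split. It is the control rate, and Section 1.2 reports response in 21 of 21 *TP53*-mutated patients on decitabine, under a broader definition and including MDS. No particular split is justified, so the ceiling is the safe figure.

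**Conclusion.** The concern holds, mainly for Cmax and the missing plasma sample. 15.4.G powers two comparisons on 100 evaluable patients in a 60-patient trial. The 85% Cmax power is unattainable: at most 66.3% two-sided with SD 40 within group, and at most 80.9% on the most favourable reading. These are ceilings that assume all 60 patients are evaluable and split equally, so they are not expected values. The plasma-level analyses in 15.4.F have no listed data source.

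For methylcytosine the fault is one of statement. The group sizes cannot occur, and the time point and sidedness are missing, but the 99% is not shown to be lost. If day 10 is meant, the evaluable number is limited to Washington University patients, a count that the documents do not give.

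A reader might infer that the trial as a whole is underpowered. Nothing here supports that: the calculation for 1-year survival uses 60 and is untouched. The point should be corrected, at moderate priority, because these analyses are correlative.

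**What to change.** Reconcile 15.4.F and 15.4.G with Sections 2, 9.2, 10 and 11, by one of two routes:

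- **If pharmacokinetics is not intended:** remove the Cmax power sentence and the effect-size remark after it from 15.4.G. From 15.4.F remove only the peak-level analysis, the words on steady-state levels and the correlation with pharmacokinetic data.
- **If it is intended:** add the objective, the timed plasma sampling and the form. Restate the Cmax power for a justified split of no more than 60 evaluable patients, with about 66% as the two-sided ceiling. State the sidedness and whether SD 40 is within-group or total.

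On either route, keep the methylcytosine-versus-response analysis. In its power sentence, replace 45/55 with group sizes attainable from the 60 patients, state the time point and sidedness, and restate the power. For near-equal groups, 99% needs about 44 evaluable patients two-sided or 37 one-sided.

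The first route costs wording only. The second needs amended objectives, sample list, calendar and forms. Either way the stated 85% disappears or becomes less favourable. The enrolment target does not change.

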## **16.0 MULTICENTER REGULATORY REQUIREMENTS**

Washington University requires that each participating site sends its informed consent document to be reviewed and approved by the Washington University Regulatory Coordinator (or designee) prior to IRB/IEC submission.

Site activation is defined as when the secondary site has received official written documentation from the coordinating center that the site has been approved to begin enrollment. At a minimum, each participating institution must have the following documents on file at Washington University prior to study activation:

- Documentation of IRB approval of the study in the form of a letter or other official document from the participating institution's IRB. This documentation must show which version of the protocol was approved by the IRB.
- Documentation of IRB approval of an informed consent form. The consent must include a statement that data will be shared with Washington University, including the Quality Assurance and Safety Monitoring Committee (QASMC), the DSMC (if applicable), and the Washington University study team.
- Documentation of FWA, signed FDA Form 1572 (if applicable), and the CVs of all participating investigators.
- Protocol signature page signed and dated by the investigator at each participating site.

The coordinating center Principal Investigator (or designee) is responsible for disseminating to the participating sites all study updates, amendments, reportable adverse events, etc. Protocol/consent modifications and IB updates will be forwarded electronically to the secondary sites within 4 weeks of obtaining Washington University IRB approval. Activated secondary sites are expected to submit protocol/consent/IB modifications to their local IRBs within 4 weeks of receipt unless otherwise noted. Upon the secondary sites obtaining local IRB approval, documentation of such shall be sent to the Washington University study team within 2 weeks of receipt of approval.

Documentation of participating sites' IRB approval of annual continuing reviews, protocol amendments or revisions, all SAE reports, and all protocol violations/deviations/exceptions must be kept on file at Washington University.

The investigator or a designee from each institution must participate in a regular conference call to update and inform regarding the progress of the trial.

## APPENDIX A: Definitions for Adverse Event Reporting

**Definition:** An adverse event is any untoward medical occurrence in a clinical study subject administered a medicinal (investigational or non-investigational) product. An adverse event does not necessarily have a causal relationship with the treatment. An adverse event can therefore be any unfavorable and unintended sign (including an abnormal finding), symptom, or disease temporally associated with the use of a medicinal (investigational or non-investigational) product, whether or not related to that medicinal (investigational or non-investigational) product. (Definition per International Conference on Harmonisation [ICH]).

This includes any occurrence that is new in onset or aggravated in severity or frequency from the baseline condition, or abnormal results of diagnostic procedures, including laboratory test abnormalities.

**Grading:** the descriptions and grading scales found in the revised NCI Common Terminology Criteria for Adverse Events (CTCAE) version 4.0 will be utilized for all toxicity reporting. A copy of the CTCAE version 4.0 can be downloaded from the CTEP website.

**Attribution (relatedness), Expectedness, and Seriousness:** the definitions for the terms listed that should be used are those provided by the Department of Health and Human Services' Office for Human Research Protections (OHRP). A copy of this guidance can be found on OHRP's website:

<http://www.hhs.gov/ohrp/policy/advevntguid.html>

All serious adverse events (SAE) that occur within 30 days of the last dose of therapy will be coded using NCI CTCAE v. 4.0. Grade 3-5 laboratory abnormalities will only be considered if they do not resolve within 7 days. The incidence of treatment-emergent adverse events (number and percent of patients reporting the adverse event at least once during the study) will be summarized. In addition, adverse events will be summarized by investigator attribution of relationship to study medication and by grade.

### A. Serious Adverse Event (SAE)

**Definition of SAE:** any adverse drug experience that results in any of the following outcomes and is unrelated to infection, bleeding, or a transfusion reaction:

- Death
- A life-threatening
- Inpatient hospitalization or prolongation of existing hospitalization
- A persistent or significant disability/incapacity (i.e., a substantial disruption of a person's ability to conduct normal life functions)
- A congenital anomaly/birth defect
- A suspected transmission of any infectious agent via a medicinal product
- Any other experience which, based upon appropriate medical judgment, may jeopardize the subject and may require medical or surgical intervention to prevent one of the outcomes listed above
- It is medically important \*

\*Medical and scientific judgment should be exercised in deciding whether expedited reporting is also appropriate in other situations, such as important medical events that may not be immediately life threatening or result in death or hospitalization but may jeopardize the subject or may require intervention to prevent one of the other outcomes listed in the definition above. These should usually be considered serious.

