### 7.3 Secondary Sites Reporting Requirements

The research team at each secondary site is required to promptly notify the Washington University Sponsor-Investigator and designee of all serious adverse events (refer to Appendix A, Section D) within **1 working day** of the occurrence of the event or notification of the secondary site's PI of the event. This notification may take place via email if there is not yet enough information for a formal written report using an FDA Form 3500a (MedWatch form) and Washington University's Cover Sheet (Appendix C). A formal written report must be sent to the Washington University Sponsor-Investigator and designee within **4 calendar days (for fatal or life threatening suspected adverse reactions) or 11 calendar days (for serious unexpected, suspected adverse reaction)** of the occurrence of the event or notification of the secondary site's PI of the event. The death of a research participant that qualifies as a reportable event should be reported within **1 working day** of the occurrence of the event or notification of the secondary site's PI of the event.

The research team at a secondary site is responsible for following its site's guidelines for reporting applicable events to its site's IRB according to its own institutional guidelines. The research team at Washington University is responsible for reporting all applicable events to the FDA, and Janssen.

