## **C. Hospitalization**

For reports of hospitalization, it is the sign, symptom or diagnosis which led to the hospitalization that is the serious event for which details must be provided.

Any event requiring hospitalization or prolongation of hospitalization that occurs during the study must be reported as a serious adverse event, except hospitalizations for the following:

- Hospitalizations not intended to treat an acute illness or adverse event (e.g., social reasons such as pending placement in long-term care facility)
- Surgery or procedure planned before entry into the study. [Note: Hospitalizations that were planned before the start of data collection and where the underlying condition for which the hospitalization was planned has not worsened will not be considered serious adverse events. Any adverse event that results in a prolongation of the originally planned hospitalization is to be reported as a new serious adverse event.]
- For convenience, the investigator may choose to hospitalize the subject for the duration of the treatment period.

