### **7.7 Exceptions to Expedited Reporting**

Events that do not require expedited reporting as described in include:

- planned hospitalizations
- respite care
- events related to disease progression

Events that do not require expedited reporting must still be captured in the EDC.

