**NOTE: DEATH FOR ANY REASON SHOULD BE REPORTED AS A SERIOUS ADVERSE EVENT.**

## **B. Adverse Events of Special Interest (AESI)**

### **Definition of Adverse Events of Special Interest**

Adverse events of special interest are events that Janssen Scientific Affairs, LLC is actively monitoring as a result of a previously identified signal (even if non-serious). No adverse events of special interest will be collected for this study.

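### The SAE definition in Appendix A leaves out events related to infection, bleeding or a transfusion reaction, contradicting Section 7.5.C, so non-fatal cases can lose the SAE label and the prompt notice tied to it

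*Combined protocol and SAP*

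**What the plan says.** The general definition, in Appendix A, part A, is "any adverse drug experience that results in any of the following outcomes and is unrelated to infection, bleeding, or a transfusion reaction". One of the outcomes listed beneath it is "A suspected transmission of any infectious agent via a medicinal product". A footnote on important medical events ends "These should usually be considered serious". The note that follows reads "DEATH FOR ANY REASON SHOULD BE REPORTED AS A SERIOUS ADVERSE EVENT".

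Section 7.5.C, in the part on reporting to Janssen, says "Any event requiring hospitalization or prolongation of hospitalization that occurs during the study must be reported as a serious adverse event". It has three exceptions: stays not meant to treat an acute illness, procedures planned before entry, and stays for convenience during treatment.

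The introduction to Appendix A adds, for attribution, expectedness and seriousness, that "the definitions for the terms listed that should be used are those provided by the Department of Health and Human Services" (through its office for human research protections).

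Section 7.3 gives secondary sites 1 working day to notify the coordinating center of "all serious adverse events (refer to Appendix A, Section D"). Section 7.5.F gives the principal investigator 24 hours to send SAEs and special situations to Janssen.

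**The concern.** Whether an event is serious should have one answer within a protocol, because the reporting clocks start from that label. Here the general definition removes three causes that a specific rule elsewhere leaves in.

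The causes are not marginal. Section 7.0 describes infection and bleeding as frequent complications of cytopenia in these patients, and Section 1.3 names infection and cytopenias as the commonest source of early death. If the general definition is followed, a non-fatal serious case can be handled as non-serious, and those who oversee the trial may hear of it later than the plan intends.

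**Working it through.** No design figure is involved, so the check sets the passages side by side.

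**Is the event an SAE?**

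- *Non-fatal infection leading to an unplanned admission.* Appendix A, part A: a listed outcome is met, but the event is related to infection, so it is not an SAE. Section 7.5.C: it is an SAE, and no exception applies. This is a direct contradiction. A bleed or a transfusion reaction gives the same result.
- *Death from infection or bleeding.* The definition would exclude it, but the note on deaths restores it. Settled.
- *Suspected transmission of an infectious agent by the product.* The lead-in excludes it and the list includes it. Section 7.5.F names it as a special situation, so notice to Janssen is settled, but the definition still contradicts itself.
- *Non-fatal, life-threatening or disabling bleed without a new or longer hospital stay.* Appendix A, part A: not an SAE. Section 7.5.C does not apply. If it is an unexpected, life-threatening suspected reaction, Appendix C gives it its own rows: 24 hours to Janssen and 4 calendar days from site to coordinating center. Otherwise nothing restores the label.
- *Event that jeopardizes the patient or is medically important.* The footnote's wording fits both of these list items and leaves room to call the event serious. It does not say that it overrides the exclusion.

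**What depends on the label?**

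- *Site to coordinating center.* Section 7.3 sets 1 working day for all SAEs. The secondary-site table in Appendix C, however, sends an SAE that needs no expedited reporting through routine data entry. These two do not agree, so the label alone does not guarantee prompt notice.
- *Janssen.* Section 7.0 requires all events to be reported as Section 7.5 sets out. Sections 7.5.C and 7.5.F together keep hospitalized cases on the 24-hour path. A case that is neither hospitalized nor labelled SAE falls to Section 7.5.G, whose timeframe is in a funding agreement outside the documents.
- *FDA.* Section 7.6 sets 15 calendar days for suspected reactions that are both serious and unexpected, and refers to Appendix A. The matching secondary-site report, 11 calendar days in Section 7.3 and Appendix C, uses the same word. An unexpected, drug-related, non-fatal infection or bleed might fail the test of seriousness under part A.

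**Where are readers sent?** Four cross-references are wrong.

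- Section 7.0 sends the Washington University team to Section 1.1, which is the Introduction.
- Section 7.0 sends secondary sites to Section 1.2, which is the Study Rationale.
- Section 7.3 cites part D of Appendix A for SAEs, but part D defines a life-threatening experience and carries no exclusion for infection or bleeding.
- Section 7.3 places the cover sheet in Appendix C; it is Appendix D.

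**The case against.** The strongest reply is that the exclusion is deliberate. These complications are expected, and expedited reports of each would add noise. That may be so, but no passage says it, and Section 7.5.C still contradicts it. Relief for expected events concerns how fast to report; it does not need a narrower meaning of serious.

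A second reply is that Section 7.5.C binds only reporting to Janssen. In that case two SAE definitions operate without the protocol saying so. Secondary-site events reach Janssen through the coordinating center, so the site's classification still matters. If Section 7.5.C is instead read as general, it settles hospitalized cases for site notice as well. The text supports either reading.

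A third reply is that nothing is lost. This stands as far as capture goes. Section 11.0 requires forms at the time of any adverse event and of any hospitalization, Appendix C sends non-expedited events through routine data entry, unanticipated problems have their own route, and Section 13.0 has the principal investigator and coordinator watch for serious toxicity continuously.

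A reader might infer more than the documents support:

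- *That Section 7.7 also contradicts the definition.* It does not. Its list begins "Events that do not require expedited reporting as described in include", which need not be exhaustive, so its silence on these causes is not a conflict.
- *That the reference to federal guidance sets a different rule.* Its text is not in the documents. It shows a competing source and no more.
- *That sites will in fact label events differently.* All sites are sent to the same Appendix A. The text allows divergence but does not show it.
- *That the wrong cross-references are a separate safety failure.* Taken alone they are clerical, and the table of contents titles Section 7.3 and Appendix D correctly.

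**Conclusion.** The contradiction between Appendix A, part A, and Section 7.5.C is on the face of the text, as is the conflict within the outcome list. It covers non-fatal events related to infection, bleeding or a transfusion reaction. Such an event, if not labelled SAE, can miss the 1-working-day site notice and, when not hospitalized, the 24-hour Janssen notice. An effect on reports of serious unexpected reactions is possible but less certain. The conclusion assumes that some readers apply part A as written and that no other document settles which passage governs.

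The size is confined to classification and timeliness. A reader might try to measure it by counting outcome types left unsettled. That fails, because the footnote reaches more than one item, unexpected life-threatening reactions have their own rows, and Section 7.5.C may settle hospitalized cases. A reader might also multiply the 60 planned patients by the 9% sepsis or 7% bacteremia quoted in Section 1.3. Those rates come from elderly AML patients and do not separate fatal from non-fatal or hospitalized from other cases, so they give no count of affected notices. The primary endpoint is untouched. The point should be fixed because the protocol itself calls these complications frequent.

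**What to change.** 1. Delete the exclusion phrase from the SAE definition in Appendix A, part A, so that seriousness agrees with Section 7.5.C and the note on deaths. State that this one definition governs all recipients.
2. If relief is intended for expected infections, bleeds or transfusion reactions, write it as an exception to expedited reporting in Section 7.7. Reconcile it with Sections 7.5.C and 7.5.F and the expedited table in Appendix C.
3. Reconcile Section 7.3 (all SAEs within 1 working day) with the secondary-site table in Appendix C (some SAEs by routine data entry). Without this, step 1 may not secure prompt notice.
4. Correct the cross-references: in Section 7.3, part D to part A and Appendix C to Appendix D; in Section 7.0, Sections 1.1 and 1.2 to the relevant parts of Section 7, which for secondary sites is 7.3.

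The cost is amendment wording, a notice to sites and some additional SAE records, many of which Section 7.5.C already requires. Step 2, if wanted, adds the work of reconciling those passages.
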